5.5.5 Cycle 4 Medications

Cycle 4 Day 1:

- A 5 to 28-day supply of venetoclax at the appropriate dose level will be distributed to the subject
- 14 doses (28-day supply) of CC-486 at the appropriate dose level will be distributed to the subject.
- Obinutuzumab 1000 mg IV (expansion and dose-finding cohorts)

Cycle 4 Day 8:

• Obinutuzumab 1000 mg IV (expansion cohort only)

Cycle 4 Day 15:

• Obinutuzumab 1000 mg IV (expansion cohort only)

5.6 CYCLE 5-9 VISITS

Patients will be assessed and/or treated in the clinic at the appropriate study site on Day 1 of the 28-day Cycles 5, 6, 7, 8, and 9. Visits should ideally occur exactly on the scheduled date, but are permitted to be rescheduled within a window of \pm 3 days.

5.6.1 Cycle **5-9** Methods and Procedures

Visits during Cycles 5-9 will take place in the oncology clinic space at participating trial sites. A focused medical history will be obtained and recorded in the clinical record by the treating investigator or qualified designee, as well as any changes in concomitant medical conditions, current medications, allergies, or social history. Current symptoms will be elucidated and recorded in the clinical record.

5.6.2 Cycle 5-9 Scales and Assessments

The treating investigator or qualified designee will take vital signs including temperature, pulse, respiratory rate, weight and blood pressure. The body mass index (BMI) and body surface area (BSA) will be calculated.

- The treating investigator or qualified designee will assess ECOG status (Appendix B) at each visit
- Prior to the Cycle 7 Day 1 visit, the second interim PET imaging for disease response (primary outcome assessment) must be completed. See Appendix E for details of PET interpretation and response assessment.
- A blood sample is to be provided to the main University of Chicago site for circulating methylation profiling (see Section 5.10) on Cycle 6 Day 1 only.

5.6.3 Cycle 5-9 Examinations and Questionnaires

The treating investigator or qualified designee will perform a focused physical exam during each visit. Clinically significant abnormal findings should be recorded as medical history. The treating investigator or qualified designee may use standard intake forms to facilitate the collection of changes in medical history, and medication list. These must be verified in a face-to-face encounter. No additional questionnaires are required.

5.6.4 Cycle 5-9 Laboratory Studies

On Day 1 of Cycles 5-9, the following studies should be obtained and reviewed prior to administration of any treatment scheduled for that day:

a) Complete blood count (CBC) with differential counts including hemoglobin, hematocrit, red blood cell count, mean corpuscular volume, white blood cell count, platelet count, absolute and relative neutrophil count, absolute and relative lymphocyte count, absolute and relative monocyte count, and absolute and relative eosinophil count.

- b) Complete metabolic panel including serum glucose, sodium, potassium, chloride, bicarbonate, blood urea nitrogen, creatinine, total protein, albumin, alanine transaminase, aspartate transaminase, and alkaline phosphatase.
- c) Serum lactate dehydrogenase level.
- d) Serum uric acid level.
- e) Serum beta-2 microglobulin level.

5.6.4 Cycle 5-9 Medications

Cycle 5 Day 1:

- A 5 to 28-day supply of venetoclax at the appropriate dose level will be distributed to the subject
- 14-day supply of CC-486 at the appropriate dose level will be distributed to the subject.
- Obinutuzumab 1000 mg IV

Cycle 6 Day 1:

- A 5 to 28-day supply of venetoclax at the appropriate dose level will be distributed to the subject
- 14-day supply of CC-486 at the appropriate dose level will be distributed to the subject.
- Obinutuzumab 1000 mg IV

Cycle 7 Day 1:

- A 5 to 28-day supply of venetoclax at the appropriate dose level will be distributed to the subject
- 14-day supply of CC-486 at the appropriate dose level will be distributed to the subject.
- Obinutuzumab 1000 mg IV

Cycle 8 Day 1:

- A 5 to 28-day supply of venetoclax at the appropriate dose level will be distributed to the subject
- 14-day supply of CC-486 at the appropriate dose level will be distributed to the subject.
- Obinutuzumab 1000 mg IV

Cycle 9 Day 1:

- A 5 to 28-day supply of venetoclax at the appropriate dose level will be distributed to the subject
- 14-day supply of CC-486 at the appropriate dose level will be distributed to the subject.
- Obinutuzumab 1000 mg IV

5.7 CYCLE 10-12 VISITS

Patients will be assessed and/or treated in the clinic at the appropriate study site on Day 1 of the 28-day Cycles 10, 11, and 12. Visits should ideally occur exactly on the scheduled date, but are permitted to be rescheduled within a window of +/- 3 days.

5.7.1 Cycle 10-12 Methods and Procedures

Visits during Cycles 10-12 will take place in the oncology clinic space at participating trial sites. A focused medical history will be obtained and recorded in the clinical record by the treating investigator or qualified designee, as well as any changes in concomitant medical conditions, current medications, allergies, or social history. Current symptoms will be elucidated and recorded in the clinical record.

5.7.2 Cycle 10-12 Scales and Assessments

The treating investigator or qualified designee will take vital signs including temperature, pulse, respiratory rate, weight and blood pressure. The body mass index (BMI) and body surface area (BSA) will be calculated.

• The treating investigator or qualified designee will assess ECOG status (Appendix B) at each visit.

5.7.3 Cycle 10-12 Examinations and Questionnaires

The treating investigator or qualified designee will perform a focused physical exam during each visit. Clinically significant abnormal findings should be recorded as medical history. The treating investigator or qualified designee may use standard intake forms to facilitate the collection of changes in medical history, and medication list. These must be verified in a face-to-face encounter. No additional questionnaires are required.

5.7.4 Cycle 10-12 Laboratory Studies

On Day 1 of Cycles 10-12, the following studies should be obtained and reviewed prior to administration of any treatment scheduled for that day:

- a) Complete blood count (CBC) with differential counts including hemoglobin, hematocrit, red blood cell count, mean corpuscular volume, white blood cell count, platelet count, absolute and relative neutrophil count, absolute and relative lymphocyte count, absolute and relative monocyte count, and absolute and relative eosinophil count.
- b) Complete metabolic panel including serum glucose, sodium, potassium, chloride, bicarbonate, blood urea nitrogen, creatinine, total protein, albumin, alanine transaminase, aspartate transaminase, and alkaline phosphatase.
- c) Serum lactate dehydrogenase level.
- d) Serum uric acid level on Day only, repeat as needed (see Appendix G).
- e) Serum beta-2 microglobulin level on Day 1 only.

5.7.5 Cycle 10-12 Medications

Cycle 10 Day 1:

- A 5 to 28-day supply of venetoclax at the appropriate dose level will be distributed to the subject
- 14-day supply of CC-486 at the appropriate dose level will be distributed to the subject.
- Obinutuzumab 1000 mg IV (expansion cohort only)

Cycle 11 Day 1:

- A 5 to 28-day supply of venetoclax at the appropriate dose level will be distributed to the subject
- 14-day supply of CC-486 at the appropriate dose level will be distributed to the subject.
- Obinutuzumab 1000 mg IV (expansion cohort only)

Cycle 12 Day 1:

- A 5 to 28-day supply of venetoclax at the appropriate dose level will be distributed to the subject
- 14-day supply of CC-486 at the appropriate dose level will be distributed to the subject.
- Obinutuzumab 1000 mg IV (expansion cohort only)

5.8 END OF TREATMENT VISIT

The end of treatment visit will be scheduled in the clinic at the appropriate study site within one calendar month of the last administered treatment (Cycle 12, Day 28). Patients who discontinue therapy due to adverse events or disease progression will be moved immediately to the end-of-treatment visit.

5.8.1 End of Treatment Methods and Procedures

An updated complete medical history will be obtained and recorded in the clinical record by the treating investigator or qualified designee, as well as any changes in concomitant medical conditions, current medications, allergies, or social history. Current symptoms will be elucidated and recorded in the clinical record.

5.8.2 End of Treatment Scales and Assessments

The treating investigator or qualified designee will take vital signs including temperature, pulse, respiratory rate, weight and blood pressure. The body mass index (BMI) and body surface area (BSA) will be calculated.

- The sponsor-investigator or qualified designee will assess ECOG status (Appendix B) at each visit.
- A CT scan with intravenous contrast of the chest, abdomen, pelvis (as well as the neck if previously involved with disease) is recommended at the time of the end-of-treatment visit as a standard-of-care disease assessment approximately one year into therapy, but is not required per the study protocol.
- A blood sample is to be provided to the main University of Chicago site for circulating methylation profiling (see Section 5.10)

5.8.3 End of Treatment Examinations and Questionnaires

The treating investigator or qualified designee will perform a focused physical exam during each visit. Clinically significant abnormal findings should be recorded as medical history. The treating investigator or qualified designee may use standard intake forms to facilitate the collection of changes

in medical history, and medication list. These must be verified in a face-to-face encounter. No additional questionnaires are required.

5.8.4 End of Treatment Laboratory Studies

At the end of treatment visit, the following studies should be obtained:

- Complete blood count (CBC) with differential counts including hemoglobin, hematocrit, red blood cell count, mean corpuscular volume, white blood cell count, platelet count, absolute and relative neutrophil count, absolute and relative lymphocyte count, absolute and relative monocyte count, and absolute and relative eosinophil count.
- Complete metabolic panel including serum glucose, sodium, potassium, chloride, bicarbonate, blood urea nitrogen, creatinine, total protein, albumin, alanine transaminase, aspartate transaminase, and alkaline phosphatase.
- Serum lactate dehydrogenase level.
- Serum beta-2 microglobulin level.

5.8.5 End of Treatment Medications

Antiviral prophylaxis may be continued for up to 6 months following the end of treatment, within the judgment of the treating investigator. Antibiotic and antifungal prophylaxis may be discontinued when any ongoing neutropenia improves to Grade 1-2 or better. TLS prophylaxis, if still ongoing this point, may be discontinued after the last dose of venetoclax or obinutuzumab.

5.9 Post Treatment Follow Up

Post-treatment follow-up visits shall occur every 8-12 weeks until 18 months post-treatment, and every 6 months thereafter until the subject is lost to follow-up, dies, withdraws from the study protocol, or the end of the study is reached. Patients who discontinue therapy due to adverse events or disease progression will be moved immediately to the end-of-treatment visit and then the post-treatment follow-up schedule. Procedures for early subject withdrawal and data collection from withdrawn patients can be found in Section 3.12 and Section 3.13.

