1.2.3.2 Secondary Objectives of the Expansion Cohort

a) Determine median overall survival (OS) and median progression-free survival (PFS) of patients treated at the MTD/RP2D.

Hypothesis: Prior studies of front-line therapies have demonstrated 5-year PFS and OS of 50% and 90% at 5 years, and 3-year PFS of approximately 75% (Tomita et al. 2013; Morschhauser et al. 2018). Our study will demonstrate expected PFS greater than 75% at the study conclusion, and estimates of 5 year PFS and OS greater than 50% and 90%, respectively.

b) Determine CR rate at 30 months after initiation of therapy (CR30) as defined by Lugano Criteria and assessed with PET-CT whole-body scan.

Hypothesis: Using the CR30 as a surrogate for PFS as previously defined (Shi et al. 2017) will yield estimates for 5-year PFS in excess of 50%.

c) In the expansion cohort, determine the CR rate (by Lugano Criteria) of combination oral therapy, assessed with PET-CT whole-body scan after 3 cycles of venetoclax/CC-486 alone.

Hypothesis: Venetoclax monotherapy and the combination of venetoclax and rituximab in relapsed/refractory FL have shown CRrates of 14% (Davids et al. 2017). In the first-line setting, the combination of venetoclax and obinutuzumab produced a CR rate of 45% (95% CI: 17% - 77%) (Stathis et al. 2019). Given the shorter 3 month window to imaging and the lack of previous trial data for the combination of venetoclax and CC-486, we hypothesize the oral combination will have a CR superior to 25% as measured by whole-body PET/CT imaging.

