2.8 SECONDARY STUDY ENDPOINTS

- Overall survival both at the end of the trial and as a 5-year estimate
- Progression-free survival both at the end of the trial and as a 5-year estimate
- "CR30" complete metabolic response rate at 30 months post-treatment initiation
- Three-month CR rate after 3 cycles of treatment with venetoclax and CC-486 alone (expansion cohort only)

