3.11 SUBJECT WITHDRAWAL FOLLOWING STUDY COMPLETION

The final study assessment will be at 30 months post initiation of treatment (18 months following treatment completion) and will consist of a clinical assessment, laboratory, and imaging studies as detailed in the Study Schema (Appendix A) and Section 5.7. After the end of treatment, each subject will be followed for the occurrence of adverse events and ongoing disease response with post-treatment visits and assessments as outlined in detail in Section 5.8. Post-treatment visits will continue until the study formally ends, the patient dies, the patient experiences disease progression requiring an alternative therapy, or the subject voluntarily withdraws prior to study completion.

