3.13 DATA COLLECTION AND FOLLOW-UP ON EARLY TREATMENT TERMINATION SUBJECTS

Subjects who are withdrawn from active treatment due to an AE or an SAE will remain enrolled in the trial for the purposes of tracking ongoing toxicity. Subjects will continue with the usual schedule of follow-up visits as feasible and will be included in the intention-to-treat analysis. Subjects who have voluntarily withdrawn from the active treatment will be asked to continue scheduled evaluations, complete an end-of-study evaluation, and be given appropriate care under medical supervision until the symptoms of any AE resolve or the subject's condition becomes stable.

Subjects who discontinue treatment for reasons other than disease progression will have post-treatment follow-up for disease status until disease progression, initiating a non-study cancer treatment, withdrawing consent, or becoming lost to follow-up. All subjects, including those who withdraw due to disease progression or complete the planned follow-up period, will be followed by telephone until death, withdrawal of consent, or the end of the study.

Subjects may be replaced in the trial as needed to ensure that the required number of evaluable subjects is achieved for the designated statistical analyses as put forth in Section 6.

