5.9.2 Post Treatment Scales and Assessments

The treating investigator or qualified designee will take vital signs including temperature, pulse, respiratory rate, weight and blood pressure. The body mass index (BMI) and body surface area (BSA) will be calculated.

• The treating investigator or qualified designee will assess ECOG status (Appendix B) at each visit.

- A CT scan with intravenous contrast of the chest, abdomen, pelvis (as well as the neck if previously involved with disease) is recommended at the time of the end-of-treatment visit as a standard-of-care disease assessment at approximately 18 months following treatment initiation (6 months post treatment competition), but is not required per the study protocol.
- A blood sample is to be provided to the main University of Chicago site for circulating methylation profiling (see Section 5.10) at approximately 18 months following treatment initiation (6 months post treatment completion) and again at 30 months post treatment initiation (18 months post treatment completion).
- At 30 months post treatment initiation (18 months post treatment completion) PET imaging for disease response (secondary outcome assessment) must be completed. See Appendix E for details of PET interpretation and response assessment.

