6.3 Subject Population(s) for Analysis

In the dose finding cohort, all enrolled patients who receive investigational agents will be subjected to study analysis. The all-treated population will be analyzed for the primary study outcomes of safety, tolerability and RP2D. In the expansion cohort, the intention-to-treat population of patients assigned to the treatment arm and who received at least one dose of an investigational agent will be used for analysis of the primary study outcome of CR rate as well as all secondary outcomes. The evaluable population will include patients who have completed 3 cycles of treatment and have a first interim response assessment data available, as well as patients with early progression and off-schedule disease assessment.

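### CR30 does not require freedom from progression and new lymphoma therapy, so a response reached on later treatment can count as a success for an endpoint meant to stand in for PFS

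*Combined protocol and SAP*

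**What the plan says.** **Definition.** Section 1.2.3.2(b) gives the objective: "Determine CR rate at 30 months after initiation of therapy (CR30) as defined by Lugano Criteria and assessed with PET-CT whole-body scan". Section 2.8 lists the endpoint as the "complete metabolic response rate at 30 months post-treatment initiation". The study summary and the Appendix A schedule add no condition. Appendix E describes scoring the most metabolically active lesion on each scan, with uptake compared to baseline. Its text carries nothing forward from an earlier progression or an intervening treatment. (Its flow diagram is not reproduced in the copy reviewed.)

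**Intended use.** The hypothesis in 1.2.3.2(b) begins "Using the CR30 as a surrogate for PFS as previously defined" and goes on to expect estimates of 5-year PFS above 50%. Section 1.2.3.3(c) also relates minimal residual disease to the 30-month response.

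**Who is scanned.** Section 5.9: "Patients who discontinue therapy due to adverse events or disease progression will be moved immediately to the end-of-treatment visit and then the post-treatment follow-up schedule". Visits under 5.9 stop only at loss to follow-up, death, withdrawal or study end. Section 5.9.2 adds: "At 30 months post treatment initiation (18 months post treatment completion) PET imaging for disease response (secondary outcome assessment) must be completed". Section 3.11, however, lists among the events that end post-treatment visits that "the patient experiences disease progression requiring an alternative therapy". Section 3.13 provides disease-status follow-up for patients who stop for reasons other than progression and ends it at progression or non-study treatment. It adds that all subjects, including those who withdraw for progression, "will be followed by telephone until death, withdrawal of consent, or the end of the study".

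**Analysis set.** Section 6.3 says that the treated intention-to-treat population of the expansion cohort "will be used for analysis of the primary study outcome of CR rate as well as all secondary outcomes". Neither 6.3 nor the rest of Section 6 says how to score a patient who progressed, changed therapy, died or was not scanned.

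**The concern.** Study treatment lasts 336 days (section 2.4), and the protocol places the CR30 scan 18 months after treatment completion. Some patients can be expected to progress and start another regimen in that interval. Under 5.9 and 5.9.2 such a patient stays on the schedule and is due a PET at month 30. If it is negative, the written definition makes the patient a CR30 success.

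That breaks the link the protocol relies on. Progression is already a PFS event, so a surrogate for PFS should record a failure. Counting the later response credits the study regimen with another treatment's effect, and the error can only raise CR30. The same misclassified patients would enter the residual-disease analysis.

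A site that follows 3.11 and 3.13 may not scan this patient at all. CR30 then depends partly on which section each site reads, and the statistician has no written rule for the empty cell.

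**Working it through.** **1. The plan's own figures.** The only powered design is for the 6-month CR rate: stop if there are 5 or fewer responses in 15, reject if there are 13 or more in 32, with p0 = 0.30 and p1 = 0.50 (sections 6.1 and 6.2.2). With X1 ~ Bin(15, p) and X2 ~ Bin(17, p):

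- Early stopping under H0 = P(X1 ≤ 5 | 0.30) = 0.7216 (stated 72.16%).
- α = Σ over x = 6 to 15 of P(X1 = x) · P(X2 ≥ 13 − x) at p = 0.30 = 0.0997 (stated 0.0997).
- Power, the same sum at p = 0.50 = 0.8038 (stated 0.8038).

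The design reproduces and does not use the month-30 scan. The protocol gives no target rate, test or power for CR30, so there is no CR30 figure to reproduce.

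**2. One patient under each set of sections.** Take a patient who progresses on treatment, starts non-study therapy and is in metabolic CR at month 30.

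| Sections followed | 30-month PET | CR30 as written |
|---|---|---|
| 5.9 and 5.9.2 | Required | Success |
| 3.11 and 3.13 | Visits and disease-status follow-up have ended | No value; no scoring rule |
| PFS | Not applicable | Event |

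**3. Number of failures by month 30 (illustration).**

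- Section 1.2.3.2(a) cites a 3-year PFS of about 75% from prior studies. Under an assumed constant hazard, 30-month PFS = 0.75^(30/36) = 0.787. Failures = 32 × (1 − 0.787) = 6.8, about 7.
- Milder assumption: 90% progression-free at month 30. Failures = 32 × 0.10 = 3.2, about 3.

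**4. Inflation from crediting later therapy.** With f failures, all scanned, and a share s of them in CR after new therapy, CR30 rises by f × s / 32 whatever the true rate. The documents give no value for s; 30% to 50% is assumed. Products are expected counts.

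| f | s | f × s | Added to CR30 |
|---|---|---|---|
| 3 | 0.30 | 0.9 | 2.8 points |
| 3 | 0.50 | 1.5 | 4.7 points |
| 7 | 0.30 | 2.1 | 6.6 points |
| 7 | 0.50 | 3.5 | 10.9 points |

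For example, a true CR30 of 16/32 = 50% would read (16 + 2.1)/32 = 56.6% to (16 + 3.5)/32 = 60.9% with 7 failures.

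**5. The other branch.** If the 7 failures are not scanned and the 6.3 denominator is kept, they add nothing to the numerator: 16/32 = 50%, with no inflation. If sites differ in which sections they follow, the result lies between zero and the values in step 4.

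**The case against.** **Dropping failures.** A reader might infer that unscanned progressors would leave the calculation, so that 16/32 = 50% becomes 16/25 = 64%. The documents do not support that as the plan. Section 6.3 assigns the treated intention-to-treat set to all secondary outcomes, and CR30 is one, so removing patients would depart from the stated denominator. What stands is narrower: no sentence says that a missing 30-month PET is non-CR30.

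**Section 5.9 cross-refers to 3.12 and 3.13.** It points there for early withdrawal and for data collection from withdrawn patients, which makes scanning after new therapy less likely in practice. The conflict remains: 5.9 itself puts progressors on the visit schedule, 3.12 keeps them monitored in the study, and 3.11 and 3.13 end visits or disease-status follow-up. It would also go too far to read 3.13 as telephone contact only. It provides telephone follow-up for all subjects and does not say that this replaces visits.

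**The cited definition.** The reference to an earlier definition of CR30 points to an outside surrogate-endpoint analysis, which may contain the missing condition. It cannot be checked here, and the protocol does not restate one.

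**Size.** The 75% figure is historical, and the plan hopes for PFS above 75% at study conclusion, so 7 failures is towards the pessimistic end. Some failures will be deaths or patients not yet needing treatment, and not all will be scanned. These points stand, and they make 11 points an upper figure within the stated assumptions.

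**Consequence.** CR30 drives no decision, PFS is reported separately, and section 2.4 already collects progression, death and next treatment, so the right rule could be applied at analysis. That is a reason the fix is cheap, not a reason to leave the rule unwritten.

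**Conclusion.** The concern holds for the definition of CR30 and for the conflict between follow-up sections. As written, a complete response after progression and non-study therapy is a CR30 success, which contradicts the use of CR30 as a PFS surrogate. Sections 5.9 and 5.9.2 disagree with 3.11 and 3.13 on whether such a patient is scanned.

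The inflation is about 3 to 11 points, assuming that 3 to 7 of 32 patients fail by month 30, that all of them are scanned, and that 30-50% are then in CR. It is zero if none is scanned and the 6.3 denominator is kept. For scale, the exact 95% interval around 17/32 (53.1%) runs from 34.7% to 70.9%. The shift is therefore smaller than sampling error, but it goes in one direction only.

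The primary endpoint, the sample size and the Simon stopping rules are not affected. This should be corrected, but it does not threaten the trial's main conclusion.

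**What to change.** - In 1.2.3.2(b), 2.8 and 5.9.2, define CR30 as complete metabolic response on the 30-month PET with no earlier progression, death or non-study lymphoma therapy.
- In 6.3, state that all dosed expansion patients stay in the CR30 denominator and that progression, death or non-study lymphoma therapy before the scan counts as non-CR30.
- Count any other missing 30-month PET as non-CR30 in the main analysis. Add a sensitivity analysis, because that rule lowers the rate for patients lost while in remission.
- Reconcile 5.9 with 3.11 and 3.13 on whether patients who have progressed have the 30-month PET. With the definition above, CR30 is scored the same way whichever rule is adopted.

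The cost is a wording amendment, best made before any month-30 data are read. The CR30 definition needs no extra patients or scans, since progression, death and next treatment are already collected under section 2.4. The downside is that the reported CR30 may be somewhat lower.

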4.2.5 Dose Modification Guidelines for Expansion Cohort

General principals/stopping rules: Dose Levels for the phase I portion of the study are as per Table 2. During the Expansion Cohort portion of the trial, dose delays/modifications are per the tables below and should be used as long as patients are deriving clinical benefit from the treatment regimen. Once the dose of an agent has been reduced, no dose re-escalation is permitted. If a scheduled dose is delayed for more than 6 weeks due to treatment-related toxicity, remove the patient from protocol therapy. No more than three dose reductions are permitted. A missed dose should not be made up, so that cycle lengths are always 28 days irrespective of the number of doses delivered in that cycle.

There will be no dose reductions for obinutuzumab. Dose reductions for CC-486 and venetoclax are per Table 4 below.

NOTE: Dose delays/dose reductions for the Dose Expansion portion of the study will be re-evaluated at the conclusion of the phase I portion of the study, and the following section is subject to revision.

Table 3A. Dose Modifications for Hematologic Toxicities. See Dose Levels for venetoclax and CC-486 in Table 4.

Observation	Action	Comments
Neutropenia ≥ gr 3	 Hold venetoclax, CC-486, and obinutuzumab (if applicable) Resume therapy at same dose level once neutropenia resolves to ≤ grade 2 If recurs, reduce by one dose level. If recurs again, reduce by one additional dose level. If recurs again, reduce by one additional dose level. 	Monitor CBC weekly. Consider use of growth factor support. If treatment is delayed by more than 6 weeks due to treatment-related toxicity, remove patient from study No more than 3 dose reductions are allowed
Thrombocytopenia ≥ gr 3	 Hold venetoclax, CC-486, and obinutuzumab (if applicable) Resume therapy at same dose level once thrombocytopenia resolves to ≤ grade 2 If recurs, reduce by one dose level. If recurs again, reduce by one additional dose level. If recurs again, reduce by one additional dose level. 	Monitor CBC weekly. No more than 3 dose reductions are allowed If treatment is delayed by more than 6 weeks due to treatment-related toxicity, remove patient from study

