15 APPENDICES

APPENDIX A: SCHEDULE OF STUDY EVENTS (SCHEMA)

Days	Screening	Day 1	Day 8	Day 15	Day 22	End of treatment visit	Post-treatment follow-up
Cycles (Dose finding arm)	Before C1	Cycle 1- 12	Cycle 1 only	Cycle 1, 2	Cycle 1 only	N/A	N/A
Cycles (Expansion cohort)	Before C1	Cycle 1- 12	Cycle 1, 4	Cycle 1, 2 and 4	Cycle 1 only	N/A	N/A
Window	Within 4 weeks	+/- 3 days	+/- 3 days	+/- 3 days	+/- 3 days	Within 4 weeks of last treatment	Every 8-12 weeks until 18 months post- treatment, every 6 months thereafter
Infusional therapy (obinutuzumab)		X	Cycle 1 (dose finding), Cycle 4 (expansion)	Cycle 1 (dose finding), Cycle 4 (expansion)			
Physical exam, vital signs, height, weight, performance status, BMI, BSA	X	X	X	X	X	X	X
Collection of AE		X	X	X	X	X	X
CBC, CMP, LDH	X	X	X	X	X	X	X
Beta-2 microglobulin	X	X				X	
Uric acid	X	X					
Hepatitis B and C, HIV serology	X						
Pathology review for eligibility	X						
Pregnancy testing	X	X					
PET whole body lymphoma study	X	Prior to cycle 4 and cycle 7					At 30 months after treatment initiation (CR30)
CT chest, abdomen, pelvis						X	At 18 months after treatment initiation
Oncoplus NGS panel (tumor)	X						
Blood draw for correlative studies	X	Prior to cycle 4, cycle 6				X	At 18 months and 30 months after treatment initiation

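### An expansion patient who stops for toxicity before the pre-Cycle 7 PET has no required 6-month PET but stays in the primary CR analysis, and the plan does not say how that patient is scored

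*Combined protocol and SAP*

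**What the plan says.** **When the PET is due.** Section 6.2.2 defines the primary outcome as a binary CR read by Lugano criteria from the 6-month PET. Section 5.6.2 ties that scan to a treatment visit: "Prior to the Cycle 7 Day 1 visit, the second interim PET imaging for disease response (primary outcome assessment) must be completed". Appendix A places the on-treatment PETs in the Day 1 column: "Prior to cycle 4 and cycle 7". The pre-Cycle 4 scan serves the month-3 secondary endpoint (5.5.2).

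**What happens after an early stop.** Under 5.8 and 5.9, patients who discontinue for adverse events or progression "will be moved immediately to the end-of-treatment visit and then the post-treatment follow-up schedule". At the end-of-treatment visit the only imaging is a CT, described in 5.8.2 as a "standard-of-care disease assessment approximately one year into therapy, but is not required per the study protocol". Follow-up has a further optional CT at about 18 months. At 30 months, 5.9.2 says "PET imaging for disease response (secondary outcome assessment) must be completed".

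**Who is analysed.** Section 6.3 takes expansion patients assigned to treatment "who received at least one dose of an investigational agent will be used for analysis of the primary study outcome of CR rate". Section 3.13 keeps adverse-event withdrawals in the intention-to-treat analysis and has them attend follow-up visits as feasible. It promises disease-status follow-up after non-progression stops, without method or date. Only voluntary withdrawals are asked to continue the scheduled evaluations. It also allows replacement to reach the required number of evaluable subjects.

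**Removal after long toxicity delays.** The text of 4.2.5 says "remove the patient from protocol therapy". Tables 3A and 3B say "If treatment is delayed by more than 6 weeks due to treatment-related toxicity, remove patient from study".

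**The concern.** The analysis population includes patients for whom the schedule does not require the outcome. The missing scans would not fall at random: they belong to patients who stopped for toxicity before the pre-Cycle 7 PET without progressing. Stops before the pre-Cycle 4 PET leave the same gap in the month-3 window CR.

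The stage 1 rule (stop at 5 or fewer CRs in 15) and the final rule (success at 13 or more in 32) rest on small counts, so a few unscanned patients can change the decision. The direction of the error depends on the scoring rule. Scoring them non-CR costs power and counts an unexamined responder as a failure. Replacing them can inflate the CR rate. A scan not done near month 6 cannot be obtained later.

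**Working it through.** **Inputs.** From 6.1 and 6.2.2: null CR rate 0.30, alternative 0.50, stage 1 of 15 patients, 17 more for a total of 32, stop at 5 or fewer, reject at 13 or more. From 7.2: expected discontinuation below 15%, with no split by cycle. The documents do not give the share d without a 6-month PET, so I assume 5%, 10% and 15%. The expected number is 32 × d = 1.6, 3.2 and 4.8 patients.

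**Formula.** P(success | p) = Σ over x = 6 to 15 of P(X1 = x; 15, p) × P(X2 ≥ 13 − x; 17, p), with X1 and X2 binomial.

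**The plan's own figures.** p = 0.30 gives 0.0997, and p = 0.50 gives 0.8038. The probability of stopping at stage 1 under the null is 0.7216. All three match section 6.1.

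**(a) Unscanned and scored non-CR.** With missingness independent of response, the effective rate is p(1 − d).

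| d | Rate at alternative | Power | Rate at null | False-success chance |
|---|---|---|---|---|
| 5% | 0.50 × 0.95 = 0.475 | 0.730 | 0.30 × 0.95 = 0.285 | 0.071 |
| 10% | 0.50 × 0.90 = 0.450 | 0.642 | 0.30 × 0.90 = 0.270 | 0.049 |
| 15% | 0.50 × 0.85 = 0.425 | 0.544 | 0.30 × 0.85 = 0.255 | 0.032 |

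**(b) How much scanning would recover.** If the early stoppers' CR rate on a scan were 25% (an assumption), the overall rate would be 0.50(1 − d) + 0.25d.

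| d | Overall rate | Power if scanned | Power if unscanned |
|---|---|---|---|
| 5% | 0.4875 | 0.769 | 0.730 |
| 10% | 0.475 | 0.730 | 0.642 |
| 15% | 0.4625 | 0.688 | 0.544 |

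At 10%, for example, the loss from 0.804 is 0.162, and scanning returns 0.730 − 0.642 = 0.088 of it.

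**(c) Replaced under 3.13.** If the unscanned are all true non-CRs and the CR rate in all treated patients is 0.30, the rate among those assessed is 0.30/(1 − d).

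| d | Rate among assessed | False-success chance (plan 0.0997) |
|---|---|---|
| 5% | 0.316 | 0.137 |
| 10% | 0.333 | 0.187 |
| 15% | 0.353 | 0.253 |

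Case (c) replaces every unscanned patient. Section 6.3 defines evaluable by completing 3 cycles with the first interim assessment, so a patient who stops between the two PETs would already count as evaluable. On that definition, replacement reaches mainly the earlier stops, and (c) is an outer case.

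**The case against.** **A reader might infer that the outcome is never measured in these patients.** The documents do not support that. Sections 3.11 to 3.13 keep them under observation for disease status and response, nothing forbids an unscheduled PET, and a patient who stops late in Cycle 6 may already have been scanned. Patients who stop for progression are non-CR by their disease status. What stands is that no PET is required near month 6 after a non-progression stop.

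**A reader might infer that these patients will be dropped.** Sections 3.13 and 6.3 say the opposite. The natural reading is a fixed denominator with an unproven CR counted as non-CR, a common and conservative rule that lowers the false-success chance, as (a) shows. But the plan does not state it, and the replacement clause points elsewhere.

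**The power loss can be overstated.** The 0.54 figure needs a full 15% to stop before Cycle 7, all without progression and all unscanned, when the plan expects less than 15% over the whole course. A 50% CR rate in early stoppers is also generous: expansion patients receive no obinutuzumab until Cycle 4, and 1.2.3.2 hypothesises only more than 25% for the oral pair. Finally, 6.2.2 presents 50% as the true 6-month CR rate, which could already be an all-treated rate, so discounting it is itself an assumption. These points limit the size but do not supply the missing scan or the missing rule.

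**Conclusion.** The point holds as a gap between schedule and analysis population, and it should be fixed. The primary 6-month PET is not required in expansion patients who stop for toxicity, without progression, before the pre-Cycle 7 scan. They remain in the primary analysis, and no scoring rule covers them. The month-3 PET has the same gap for stops before the pre-Cycle 4 scan.

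The design arithmetic in 6.1 is correct. The size of the effect is illustrative: power of 0.73 to 0.54 if 5% to 15% are unscanned and scored non-CR, assuming a 50% CR rate in them. If their CR rate were 25%, scanning would bring power to 0.77 to 0.69, so only part of the loss is recoverable. Under replacement of true non-CRs, the false-success chance is 0.14 to 0.25. The 15% end is an upper bound on the plan's own expectation.

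The conflicting removal wording is a separate inconsistency that bears on this one, because it decides whether a later PET can be collected.

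**What to change.** 1. Keep the pre-Cycle 4 and pre-Cycle 7 PETs for patients on treatment. A fixed calendar date for everyone could bring the scan forward of six completed cycles in patients with treatment holds, against the objective in 1.2.3.1.
2. In 3.13, 5.8, 5.9 and Appendix A, require any outstanding month-3 and 6-month PET at about 3 and 6 months from Cycle 1 Day 1, with a stated window, in every dosed expansion patient who stops early without progression. Exceptions are later progression, new anti-lymphoma therapy, death or withdrawn consent.
3. In 6.3, state that dosed patients without a qualifying 6-month PET count as non-CR in the fixed denominator, and align the replacement clause in 3.13 with this.
4. Reconcile the removal wording in Tables 3A and 3B with the text of 4.2.5 and with 3.12 and 3.13.

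The cost is protocol wording. No scans are added beyond the two already planned per patient. Some will be done off treatment and reflect shorter exposure, so those patients should be listed.
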